encourage caregivers to ask questions (e.g., increasing visit time) and ways to address those concerns (e.g. instructing caregivers to ask only questions that are of particular concern). The interviews will also address formatting considerations of the caregiver workbook and provider manual (e.g. font size, language that is easy to understand, space for notes). Caregivers will also be asked to fill out a brief questionnaire that will be sent to participants along with the PAINAD tool by email or postal mail, or given to the participant prior to their interview. The questionnaire will include demographics, caregiving role, and patient health questions. Participants will be provided a self-addressed stamped envelope to mail this survey back; or they can use the WCMC secure file transfer to email back the questionnaire.

Field testing. Once initial versions of the PICT manual and workbook are developed, they will be iteratively field-tested and vetted by family caregivers (n=25 per iteration) and health care providers (n=20 per iteration). Participants will be recruited at WCM/NYP locations including the Center on Aging and Weill Cornell Medical Associates. After reviewing the PICT workbook, caregivers will complete a brief questionnaire about the content, format, and perceived utility of PICT, as well as ways to enhance its cultural relevance. They will also complete a brief (15-20 minute) semi-structured interview to clarify their perspectives. Health care providers will answer a similar set of questions. Results from this first field-test will inform the modified version of PICT and will address key issues, such as the feasibility of using research nurses (and other practice staff) to administer the intervention, anticipation of participant burden for caregivers, and adequacy of PICT format and instructions. Study procedures will be repeated (including IRB approval) with a new sample of caregivers (n=25) and providers (n=20). Results from the second field-test will be used to create the finalized intervention of PICT. Prior research indicates that a feasible intervention should be generated after two iterations.

Pilot testing. Family caregivers will be randomly assigned to PICT (n=50) or a control (usual care) condition (n=50).

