Participants in both conditions will be asked to complete an identical pre-test questionnaire. The questionnaire will be sent to via email or postal mail, and/or will be scheduled to be completed over the phone. We will ask about the participant's background, caregiving role, and comfort speaking with health care providers. It will take approximately 15-20 minutes to complete.

Intervention condition. Participants in the intervention condition will be contacted by a member of the study team to start the PICT workbook. The PICT workbook consists of four sessions and will be completed over the telephone with a study team member. Sessions are conducted once a week and last approximately 30-60 minutes each. Participants will also be asked to read sections of the PICT workbook and complete exercises between sessions. The reading and exercises will take 10-15 minutes to complete. After the final session of the intervention, a study team member will contact the participant by telephone to complete another set of questionnaires (at 12 weeks after the pre-test questionnaire). The questionnaire will be sent to via email, postal mail, or will be scheduled to be completed over the phone. The post-test questionnaires will take approximately 20 minutes to complete and will ask about the participant's comfort and confidence in communicating with health care providers, behaviors he or she observes in the recipient, and views of the PICT workbook. Participants will also be asked to participate in a 20-30 minute telephone interview to elaborate their responses to the questionnaire. Participants must agree to be audiotaped to participate in the study.

Control condition. Caregivers in the control condition will receive an informational pamphlet about pain in dementia and a link to the Alzheimer's Association website. Twelve weeks after the participant completes the pre-test questionnaire, she or he will be contacted by a member of the study team to complete the post-test questionnaire. The questionnaires will be sent via email, postal mail, or will be scheduled to be completed over the phone and will take approximately 20 minutes to complete.

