7.2.5 Record Retention

Essential documents are those documents that individually and collectively permit evaluation of the study and quality of the data produced. After completion of the study, all documents and data relating to the study will be kept in an orderly manner by the Investigator in a secure studyfile. Essential documents should be retained for 2 years after the final marketing approval in an ICH region or for at least 2 years since the discontinuation of clinical development of the IP. In addition, all subject medical records and other source documentation will be kept for the maximum time permitted by the hospital, institution, or medical practice.

8. Statistical Considerations

Interviews: Interview transcripts will be analyzed according to the constant comparative method, in which new concepts are compared to existing codes (labels that catalog key concepts), existing codes are refined, and a coding structure is developed in stages. This process will continue until theoretical saturation is reached - the point at which no new information is generated from additional interviews.

Pilot testing: statistical considerations. Feasibility will be examined in terms of rates of recruitment and number of sessions completed by participants in the intervention condition. Preliminary analyses to compare the intervention vs. control group on PWD and caregiver sociodemographic characteristics will be carried out in linear models (for continuous variables) and logistic-linear models (for categorical variables). The effectiveness of the intervention will be evaluated in a statistical model that includes treatment (control vs. intervention) and time of assessment (baseline vs. 4 weeks post intervention) as fixed classification factors; the interaction of treatment and time; covariates such as age and gender; and family caregivers (30 per treatment group) as levels of a random classification factor. The primary dependent variable (caregiver contacts primary care practice) is dichotomous, and analysis is by a logistic-linear mixed model with binomial error. Self-efficacy will be included in the model as a fixed classification factor (categorized in 2 levels) as will its interaction with treatment and time. Interactions with other key sociodemographic and clinical variables will also be examined.

9. Adverse Event Reporting Requirements

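### Self-efficacy is cut into two levels with no stated cut point or rationale, which, if it is a multi-level score, discards information on its main effect and moderation terms

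*Combined protocol and SAP*

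**What the plan says.** Section 8, pilot testing paragraph, defines the main model. "The primary dependent variable (caregiver contacts primary care practice) is dichotomous", and "analysis is by a logistic-linear mixed model with binomial error". Treatment, time and their interaction are fixed effects, and caregivers are the random factor. The plan then adds self-efficacy as a "fixed classification factor (categorized in 2 levels"; and, of the same variable, "as will its interaction with treatment and time". Self-efficacy is the only potential effect modifier named; other interactions are mentioned only in general terms.

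The documents do not name the self-efficacy instrument or its range. They give no cut point, no rationale for two levels and no rule for fixing the cut. They do not say whether the baseline or a time-varying value is used, and they plan no analysis of the uncut score. The nearest description of the data is in Section 3.1, where the pre-test questionnaire covers the caregiver's background, "caregiving role, and comfort speaking with health care providers".

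The number of caregivers differs between sections. Section 8 has "family caregivers (30 per treatment group) as levels of a random classification factor"; Section 3.1 has "Family caregivers will be randomly assigned to PICT (n=50) or a control (usual care) condition (n=50". That is a separate matter to reconcile, so both totals (60 and 100) are used below.

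**The concern.** Describing a variable as categorised suggests that a finer measure is being collapsed. Collapsing it treats all caregivers on one side of the cut as identical and treats two caregivers just either side of it as different. If the effect of self-efficacy changes gradually along the scale, the two-level factor is a noisy stand-in for the score, and its coefficients are estimated less precisely.

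What is at stake is the self-efficacy main effect and the analysis of who benefits from PICT. With 60 or 100 caregivers and a yes/no outcome, an interaction is already hard to estimate. An unspecified cut also leaves the analyst a choice. The moderation result can change with the cut, and a cut picked because it gives a strong outcome contrast yields a p-value that is too small.

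**Working it through.** The plan states no power, effect size, score distribution or cut for self-efficacy, so there is no figure of its own to reproduce. Everything below rests on stated assumptions.

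**1. Normal score, effect linear on the logit.** The share of information kept is the squared correlation between the score and its two-level version. With a proportion q below the cut c:

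kept = φ(c)² / [q(1 − q)]

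| Split | φ(c)² / [q(1 − q)] | Kept | Lost |
|---|---|---|---|
| 50/50 | 0.1592 / 0.25 = 2/π | 63.7% | 36.3% |
| 70/30 | 0.1209 / 0.21 | 57.6% | 42.4% |
| 80/20 | 0.0784 / 0.16 | 49.0% | 51.0% |

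Equivalent numbers for the self-efficacy terms at a median split are 60 × 0.637 = 38 and 100 × 0.637 = 64.

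**2. Other score shapes, near-even split.** These shapes are assumptions, because the documents give none.

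| Assumed score | Lost |
|---|---|
| U-shaped, Beta(0.5, 0.5) | 19% |
| Evenly used 4-point item, cut in the middle | 20% |
| Uniform | 25% |
| Evenly used 5-point item, split 3/2 | 25% |
| Two-peaked normal mixture | 25% |
| Left-skewed, Beta(5, 2) | 35% |
| t with 5 degrees of freedom | 46% |
| Exponential | 52% |

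As a check on one row: for a uniform score on 0–1 the covariance with its median split is 3/8 − 1/4 = 1/8, so kept = (1/8)² / (1/12 × 1/4) = 0.75.

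**3. What this does to power.** For a self-efficacy test that would have 80% power on the continuous score (an illustration, not a figure from the plan), power after the split is Φ[(1.96 + 0.842) × √kept − 1.96]. This gives 61% at a normal median split, 57% at a normal 70/30 cut and 68% at a uniform median split.

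**4. Simulated treatment-by-self-efficacy interaction.** The setting was logistic, post-test only, with no random effect, a normal score, a median split, two-sided 5% and 1,500 runs. Assumed coefficients were −0.3 (intercept), 0.6 (treatment) and 0.3 (self-efficacy), with the interaction as shown.

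| Truth | Total N | Power, continuous | Power, split |
|---|---|---|---|
| Linear, 0.8 per SD | 60 | 0.21 | 0.16 |
| Linear, 0.8 per SD | 100 | 0.35 | 0.25 |
| Linear, 1.2 per SD | 60 | 0.35 | 0.24 |
| Linear, 1.2 per SD | 100 | 0.61 | 0.43 |
| Step at the cut, 0.8 | 60 | 0.21 | 0.24 |
| Step at the cut, 0.8 | 100 | 0.34 | 0.45 |

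With no interaction, both tests rejected in 4–5% of runs. The simulation agrees with step 1. At slope 1.2 and N = 100, unrounded powers of 0.613 and 0.434 correspond to test-statistic means of 0.287 + 1.96 = 2.247 and −0.166 + 1.96 = 1.794, and (1.794 / 2.247)² = 0.64.

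**The case against.** The best defence is that the documents do not establish what is being split. No instrument is named, so a multi-level score is an inference. If self-efficacy were recorded as a yes/no item, nothing would be lost. The affected terms are also secondary: this is a pilot aimed at preliminary efficacy, and the term that tests PICT is treatment by time. Even the continuous moderation test has low power at these sizes (0.35 at N = 60 and 0.61 at N = 100 for the larger assumed slope). And if the true effect were a step at the cut, the two-level factor would do better.

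Much of this stands and limits the point. It does not supply a reason for the split or a cut, and the plan states no step. Low power for moderation is a reason not to give up more of it.

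Several stronger readings are tempting but unsupported:

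- A reader might take 36% as a minimum. It is the value for a normal score with a linear effect cut at the median; flatter or short-item scores lose 20–25%.
- A reader might take it as a loss to the trial's main comparison. It applies to the self-efficacy terms.
- A reader might infer that a continuous score is free. It needs no extra degree of freedom per term, but it assumes linearity on the logit, and curved terms would use degrees of freedom that a small trial can ill spare.
- A reader might infer that any cut taken from the data distorts the p-value. A sample median ignores the outcome and does not; the problem arises only if the outcome guides the cut, and the documents do not say how it will be chosen.
- A reader might equate self-efficacy with the pre-test comfort question. Section 3.1 does not do so.

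**Conclusion.** The point holds in a conditional form. The plan commits to a two-level factor without a cut or a rationale. If the measure has more than two levels, that is a worse choice than using the score, unless the true effect is close to a step at the cut. For a roughly normal score with a linear effect on the logit, the loss on the self-efficacy main effect and moderation terms is about 36% at the median, 42% at 70/30 and 51% at 80/20. Across the other shapes tried, near-even splits lose roughly 20–50%. The dependence of the moderation result on an unstated cut does not rely on any of these shapes. This is worth correcting before analysis, but it does not undermine the treatment-by-time comparison or invalidate the pilot.

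**What to change.** In Section 8:

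- Name the self-efficacy measure and its range, and state that the pre-test value is used. This matters because caregiver efficacy in communication is also an outcome under Objective 3.
- Replace the two-level factor with the pre-test score as a centred continuous covariate, and test moderation with that score, including its joint interaction with treatment and time.
- Check linearity on the logit with a plot.
- Report predicted PICT effects at a low, a middle and a high score, so that the result stays easy to read.
- If two levels are kept for display, fix the cut before outcomes are seen.

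The cost is a few lines of wording. If a multi-level pre-test score is already collected, no new data and no added burden on caregivers are needed. The small downside is the linearity assumption, and some loss of power relative to the split if the true effect is a step at the cut.

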9.1 Adverse Event Definition

An adverse event (also referred to as an adverse experience) can be any unfavorable and unintended sign (e.g., an abnormal laboratory finding), symptom, or disease temporally associated with the use of a drug, and does not imply any judgment about causality. An adverse event can arise with any use of the drug (e.g., off-label use, use in combination with another drug) and with any route of administration, formulation, or dose, including an overdose.

9.1.1 Adverse Event Characteristics and Related Attributions

CTCAE term (AE description) and grade: The descriptions and grading scales found in the revised NCI Common Terminology Criteria for Adverse Events (CTCAE) version 4.0 will be utilized for AE reporting. A copy of the CTCAE version 4.0 can be downloaded from the CTEP web site (<http://ctep.cancer.gov>).

- Attribution of the AE:
 - Definite – The AE *is clearly related* to the study treatment.
 - Probable – The AE *is likely related* to the study treatment.
 - Possible – The AE *may be related* to the study treatment.
 - Unlikely – The AE *is doubtfully related* to the study treatment.
 - Unrelated – The AE *is clearly NOT related* to the study treatment.

9.1.2 Recording of Adverse Events

All adverse events will be recorded on a subject specific AE log. The AE log will be maintained by the research staff and kept in the subject's research chart.

9.1.3 Reporting of AE to WCM IRB

All AEs occurring on this study will be reported to the IRB according to the IRB policy, which can be accessed via the following link:

http://researchintegrity.weill.cornell.edu/forms_and_policies/forms/Immediate_Reporting_Policy.pdf.

9.1.4 Reporting Events to Participants

Not applicable

9.1.5 Events of Special Interest

Not applicable

9.1.6 Reporting of Pregnancy

Not applicable

10. Unanticipated Problems Involving Risks to Subjects or *Others*

Not applicable

10.1 Definition of Unanticipated Problems Involving Risks to Subjects or Others (UPIRTSO)

Not applicable

